						Plasma ^b BI 891065	Plasma ^b BI 754091	██████	Biopsy ^c	██████
1	2	1	Predose (between screening and C1D1 dosing)						X	
			-30 min (+/-15min)	-30 min	X					
1	2	1	Just before drug admin	Predose ^a	X		X	X		X
			BI 754091 admin	0:00						
			Just before infusion end	1:00			X			
			1:25	1:25	X**	X	X			
			BI 891065 admin	1:30						
			2:00	2:00		X	X			
			2:30	2:30	X**	X	X			
			3:30	3:30	X**	X	X			
			4:30	4:30	X**	X	X	X		
			6:30	6:30	X**	X	X			
			7:30	7:30	X	X	X			
			8:30	8:30	X**	X	X			
			9:30	9:30	X	X	X	X		
			11:30	11:30	X**	X	X			
			No drug intake	13:30						
	3	2	Just before drug intake	25:25	X	X	X	X		
			BI 891065 intake	25:30						
	4	8	Just before drug intake	167:55		X	X	X		
			BI 891065 intake	168:00						
	5	12	Just before drug intake	263:55		X	X			
			BI 891065 intake	264:00						

ADA = anti-drug antibodies; BI = Boehringer Ingelheim; CRF = Case Report Form; IAP = inhibitor of apoptosis; PTM = planned time
 a PK to be taken following an overnight fast (minimum 10 hours) on this day
 b The following windows of time are allowed for PK and ECG sampling (ECGs should be performed PRIOR to PK sampling):

- Predose samples (PTM -0:05, 25:25, 167:55, etc.): within 1 hour before drug intake
- One hour to 4:30 hours post first drug intake (PTM 1:00 through PTM

4:30): within ±10 minutes of designated time

- 6:30 to 11:30 hours post first drug intake (PTM 6:30 through 11:30): within ±15 minutes of designated time

Time windows are specified for procedural reasons; deviations do not automatically lead to exclusion of samples from data evaluation.

c Biopsy for IAP degradation to be taken as noted in Part B Flow Chart.

* In order not to confuse an ECG recording, all PK samples should be taken after performing the ECGs.

** ECGs will be taken throughout, as it is possible that time of maximum concentration is not accurately estimated; for safety, this is one of the most relevant time points, so should not be missed. As such, some ECGs may only be evaluated at later points or, if deemed unnecessary, not at all.

Table 10.3: 3 Time schedule for PK blood, [REDACTED] sampling during Part B excluding food effect in b.i.d. treatment group (continued)

Cycle	Visit	Day	Time Point [hh:min]/event	CR F Time /PT M	Tripl icat e ECGs*	Samples				
						Plas ma ^b BI 891065	Plas ma ^b BI 754091	[REDACTED]	Bio psy ^c	[REDACTED]
1	6	15	Just before drug admin	335:55 ^a	X	X	X			
			BI 891065 intake	336:00						
			0:30	336:30	X	X				
			1:00	337:00	X**	X				
			2:00	338:00	X**	X				
			3:00	339:00	X**	X				
			5:00	341:00	X**	X				
			6:00	342:00	X	X				
			7:00	343:00	X**	X				
			8:00	344:00	X	X				
			10:00	346:00	X**	X				
			No drug intake	348:00						
	7	16	Just before drug intake	359:30**	X	X	X			
			BI 891065 intake	360:00						

	2-5, then every 2 nd cycle	9-12 then every 2 nd cycle	1	Just before drug admin	- 0:05		X (C2 only)	X		X	X
				Just before infusion end	1:00			X			
	EOT							X	X		X
	30-Day FU							X			X
	
ADA = anti-drug antibodies; BI = Boehringer Ingelheim; CRF = Case Report Form; ECG = electrocardiogram; EOT = end of treatment; FU = follow up; IAP = inhibitor of apoptosis; PTM = planned time
 
a PK to be taken following an overnight fast (minimum 10 hours) on this day
 
b The following windows of time are allowed for PK and ECG sampling (ECGs should be performed PRIOR to PK sampling):
 
 • Predose samples (PTM 335:55 [Day 15]): within 1 hour before drug intake • On Day 15 (PTM 336:30 through 339:00): within ±10 minutes of designated time • On Day 15 (PTM 341:00 through 346:00): within ±15 minutes of designated time • On Day 16 (PTM 359:30): within 30 min before drug intake 
Time windows are specified for procedural reasons; deviations do not automatically lead to exclusion of samples from data evaluation.
 
c Biopsy for IAP degradation to be taken as noted in Part B Flow Chart.
 
* In order not to confuse an ECG recording, all PK samples should be taken after performing the ECGs.
 
** ECGs will be taken throughout, as it is possible that time of maximum concentration is not accurately estimated; for safety, this is one of the most relevant time points, so should not be missed. As such, some ECGs may only be evaluated at later points or, if deemed unnecessary, not at all.
 
***Central lab kits provided will contain extra tubes (for post-dose timepoints 360:30-370:00 on Day 16 and 383:55 on Day 17). These tubes should not be used for b.i.d patients.
										
Rationale for change	To describe the PK, [REDACTED] sample collections for Part B b.i.d. patients.										
Section to be changed	Section 10.4 Pharmacokinect Analyses										
Description of change	• C _{pre,N} (pre-dose concentration of the analyte in plasma after before the Nth dose)										
Rationale for change	To correct an error in the text for the C _{pre N} collection time.										

[figure not shown]

APPROVAL / SIGNATURE PAGE

2. LIST OF ABBREVIATIONS

Term	Definition / description
ADA	Anti-drug Antibody
AE	Adverse Event
AESI	Adverse Event of Special Interest
ATC	Anatomical Therapeutic Chemical
BI	Boehringer Ingelheim
BLRM	Bayesian Logistic Regression Model
BMI	Body Mass Index
cIAP	Cellular Inhibitor of Apoptosis
CR	Complete Response
CT	Concomitant Therapy
CTCAE	Common Terminology Criteria for Adverse Events
CTP	Clinical Trial Protocol
CTR	Clinical Trial Report
DILI	Drug-induced Liver Injury
DLT	Dose-limiting Toxicity
ECG	Electrocardiogram
ECGPCS	Electrocardiogram Pharmacokinetic Concentration Set
ECOG	Eastern Cooperative Oncology Group
eCRF	Electronic Case Report Form
ES	Enrolled Set
HR	Heart Rate
ICH	International Conference on Harmonization
iCPD	Immune Confirmed Progressive Disease
iCR	Immune Complete Response
iPR	Immune Partial Response
IPD	Important Protocol Deviation
iRECIST	modified RECIST 1.1 for immune-based therapeutics
iSD	Immune Stable Disease
iUPD	Immune Unconfirmed Progressive Disease

MedDRA	Medical Dictionary for Regulatory Activities
ms	milliseconds
MTD	Maximum Tolerated Dose
NSCLC	Non-small Cell Lung Cancer
OR	Objective Response
ORR	Objective Response Rate
PBMCs	Peripheral Blood Mononuclear cells
PD	Progressive Disease
PFS	Progression-free Survival
PK	Pharmacokinetics
PKS	Pharmacokinetic Set
PR	Partial Response
PR interval	ECG interval from the onset of the P wave to the beginning of the QRS complex
PT	Preferred Term
QRS	Combination of the Q, R and S waves
QT	ECG interval from the beginning of the QRS complex to the end of the T wave
QTc	Generic term for QTcF and QTcB intervals
QTcB	QT interval, corrected by Bazett's formula
QTcF	QT interval, corrected by Fridericia's formula
RECIST	Response Evaluation Criteria In Solid Tumours
REP	Residual Effect Period
SCR	Screened Set
SD	Stable Disease
SOC	System Organ Class
SRC	Safety Review Committee
StD	Standard Deviation
TS	Treated Set
TSAP	Trial Statistical Analysis Plan
ULN	Upper Limit of Normal
WHO DD	World Health Organisation Drug Dictionary

[figure not shown]
3. INTRODUCTION

As per International Conference on Harmonisation E9 (ICH E9) (1) the purpose of this document is to provide a more technical and detailed elaboration of the principal features of the analysis described in the protocol, and to include detailed procedures for executing the statistical analysis of the primary and secondary variables and other data.

This Trial Statistical Analysis Plan (TSAP) assumes familiarity with the Clinical Trial Protocol (CTP), including Protocol Amendments. In particular, the TSAP is based on the planned analysis specification as written in CTP Section 7 “Statistical Methods and Determination of Sample Size”. Therefore, TSAP readers may consult the CTP for more background information on the study, e.g., on study objectives, study design and population, treatments, and definition of measurements and variables.

The study is a multicentre study consisting of three study parts. Part A is an open-label, dose-escalation of BI 891065 alone. Part B is an open-label dose-escalation of BI 891065 in combination with a fixed dose of BI 754091. Part C consists of an expansion cohort in non-small cell lung cancer (NSCLC).

For the primary objective of the separate parts of the trial, refer to Section 2 of the CTP.

[figure not shown]

In the following, study medication always refers to BI 891065 in Part A, and to BI 891065 and/or BI 754091 in Parts B and C.

SAS[®] Version 9.4 or higher will be used for all analyses besides pharmacokinetic (PK) analyses if not specified otherwise. WinNonlin Version 8.1 will be used for PK analyses.

4. CHANGES IN THE PLANNED ANALYSIS OF THE STUDY

All analyses described in the CTP will be carried out.

Since t_{max} of BI 891065 appears to be earlier than expected, all ECG recordings collected at the scheduled time points listed in Tables 10:3:1, 10:3:2 and 10:3:3 of the CTP will be analysed.

Part C of this trial is cancelled and enrolled no patients. Hence, no planned analyses for this trial part will be conducted.

5. ENDPOINT(S)

5.1 PRIMARY ENDPOINT(S)

Part A:

The primary endpoints for Part A of the trial are the MTD of BI 891065 and the number of patients with dose-limiting toxicities (DLTs) during the MTD evaluation period (first treatment cycle). For definition of the MTD, refer to Section 2.1.2.1 of the CTP.

Part B:

The primary endpoints for Part B of the trial are the MTD of BI 891065 in combination with BI 754091 and the number of patients with DLTs during the MTD evaluation period (first treatment cycle). For definition of the MTD, refer to Section 2.1.2.2 of the CTP.

Part C:

The primary endpoint is OR by investigator's assessment based on RECIST version 1.1 (2). For definition of OR refer to CTP Sections 2.1.2.3.

5.2 SECONDARY ENDPOINT(S)

5.2.1 Key secondary endpoint(s)

Not applicable.

5.2.2 Secondary endpoint(s)

Part A:

- The number of patients with DLTs observed during the entire treatment period
- $C_{\max,ss}$, AUC_{0-tz} and $AUC_{\tau,ss}$ of BI 891065 in the first treatment cycle
- OR by investigator's assessment based on RECIST v1.1, defined in the same way as the primary endpoint for Part C.

Part B:

- The number of patients with DLTs observed during the entire treatment period
- $C_{\max,ss}$, AUC_{0-tz} and $AUC_{\tau,ss}$ of BI 891065 in the first treatment cycle and C_{\max} and AUC_{0-tz} of BI 754091 in the first treatment cycle
- OR by investigator's assessment based on RECIST v1.1, defined in the same way as the primary endpoint for Part C.

Part C:

Secondary endpoint for Part C is the duration of OR by investigator's assessment based on RECIST v1.1.

[figure not shown]
Duration of OR is defined as:

[figure not shown]
Duration of OR [days] = date of outcome – date of attaining complete response (CR) or partial response (PR) +1,

[figure not shown]
for patients who achieve a CR or PR according to RECIST v1.1. Censoring rules and applicable dates of outcome for duration of OR according to RECIST v1.1 are specified in Table 5.2.2: 1.

[figure not shown]
Table 5.2.2: 1 Censoring rules for duration of objective response according to RECIST v1.1

[figure not shown]
Situation	Outcome (event or censored)	Date of outcome
No other anti-cancer therapy		
Alive and not progressed according to RECIST v1.1, no more than one consecutively missed radiological assessment	Censored	Date of last radiological assessment
Alive and not progressed according to RECIST v1.1, two or more consecutively missed radiological assessments	Censored	Date of last radiological assessment prior to missed radiological assessments
Progressed according to RECIST v1.1, zero or one missed radiological assessment prior to progression	Event	Date of radiological assessment of progression
Progressed according to RECIST v1.1, two or more consecutively missed radiological assessments prior to progression	Censored	Date of last radiological assessment prior to missed assessments
Death but no progression according to RECIST v1.1, zero or one missed radiological assessment prior to death	Event	Date of death
Death without progression according to RECIST v1.1, but two or more consecutively missed radiological assessments prior to death	Censored	Date of last radiological assessment prior to missed assessments
Initiation of subsequent anti-cancer therapy		
Subsequent anti-cancer therapy started before progression according to RECIST v1.1 or death, no more than one consecutively missed radiological assessments prior to start of subsequent anti-cancer therapy	Censored	Date of last radiological assessment before initiation of subsequent anti-cancer therapy

5.4 OTHER VARIABLE(S)

5.4.1 Demographics and baseline history

Only derived variables are defined here. Standard demographic and baseline characteristics will be used as recorded in the electronic case report form (eCRF).

Body Mass Index (BMI):

$$\text{BMI} \left[\frac{\text{kg}}{\text{m}^2} \right] = \frac{\text{weight} [\text{kg}]}{(\text{height} [\text{m}])^2}$$

5.4.2 Extent of Exposure

Duration of BI 891065 intake is defined as the time from first administration of BI 891065 until the last administration of BI 891065 +1 day.

The duration of BI 754091 intake will be assessed in terms of number of BI 754091 courses administered for Part B and Part C.

The time to first dose reduction of BI 891065 is defined as the time from first administration of BI 891065 to the first administration of the first reduced dose of BI 891065 +1 day.

Dose intensity (%) will be calculated as the total dose received by the patient divided by the planned total dose, where the planned total dose will be calculated as the dose that the patient should have received between the day of first administration and the date of last administration of BI 891065 (for the dose intensity of BI 891065) and BI 754091 (for the dose intensity of BI 754091), respectively. That is, the actual dose will be divided by the amount of drug that would have been administered had the protocol-specified first dose been administered at each day according to the protocol schedule until the end of treatment.

5.4.3 ECG

Clinically relevant electrocardiogram (ECG) findings will be analysed in terms of adverse events (AEs). Additionally, statistical ECG analyses will be done with variables defined as in the following paragraphs for all 3 trial parts.

Refer to [Section 7.8.4](#) for a detailed description of the derivation of ECG variables.

The generic term QTc for heart rate corrected QT intervals comprises the fixed corrections QTcF (Fridericia's correction) and QTcB (Bazett's correction). Results involving the QTcB interval will only be presented in listings in the appendix of the CTR. For ECG analyses, the on-treatment period refers to all scheduled time points with centrally evaluated ECG recordings following the first administration of trial medication in Cycle 1.

Quantitative variables

- Changes in QTcF interval between baseline and on-treatment
- Absolute QTcF intervals at baseline and on-treatment

These variables will also be computed for the uncorrected QT interval, QTcB, the heart rate, the PR interval, and the QRS complex. Furthermore, the percentage change will be calculated for PR interval and QRS complex.

Categorical variables

The following thresholds will be used for a categorization of the quantitative ECG variables for each patient per time point:

- QTc intervals ≤ 450 ms, > 450 to 480 ms, > 480 to 500 ms or > 500 ms, at baseline and for all on-treatment values
- QT intervals ≤ 500 ms, > 500 ms, at baseline and for all on-treatment values
- Change from baseline to on-treatment value in QTc interval ≤ 30 ms, 30 ms $<$ QTcF interval ≤ 60 ms, > 60 ms
- Change from baseline to on-treatment value in QT interval ≤ 60 ms, > 60 ms

For the QTcF and uncorrected QT interval, the categorizations described above will be performed separately for the visit days where an ECG profile has been taken as well as for the overall on-treatment period using the maximum value per patient within the considered period.

[figure not shown]
A notable finding in QT/QTcF interval in any on-treatment value for a given patient is defined as

[figure not shown]
- QTcF change from baseline to on-treatment value > 60 ms at any time on-treatment
- new onset of QT/QTcF > 500 ms, where “new onset” denotes the occurrence of a finding on-treatment which was not present at baseline
- Increase of the PR interval from baseline $\geq 25\%$, when the corresponding PR interval is > 200 ms
- Increase of QRS complex from baseline $\geq 25\%$, when the corresponding QRS complex is > 110 ms

Qualitative variables

- The overall interpretation of an ECG, which is classified as “normal”, “abnormal”, or “unable to evaluate”,
- New onset of morphological findings, where “new onset” denotes the occurrence of an on-treatment finding, while at baseline this finding was not reported. Among these, new onset of the following findings are of special interest: atrial flutter, atrial fibrillation, any degree or type of heart block, ST-segment changes, T wave abnormalities, new U waves and myocardial infarction pattern.

The occurrence of notable or qualitative ECG findings will also be derived for the aggregated on-treatment time points of the visit days where an ECG profile has been taken as well as for the overall on-treatment period.

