In case of related ECG changes and whenever the Investigator deems necessary, additional ECG monitoring will be performed in the respective and later courses of treatment. The ECGs will be recorded using dedicated equipment provided by a vendor. The ECGs will be sent for evaluation by a central vendor. Data from this central review will be taken for retrospective data analysis. To allow for a heart rate correction of QT intervals the QT intervals will be matched to the preceding RR intervals using at least QTcF (Fridericia's formula $QTcF = QT/RR^{-1/3}$) and QTcB (Bazett's formula $QTcB = QT/RR^{-1/2}$).

In case of QTcF prolongation to >500 ms (mean of 3 ECGs) AFTER receiving therapy, the Investigator will initiate further ECG monitoring and diagnostics (e.g., check electrolytes and check concomitant therapy that may be contributing to QTcF prolongation) and if required provide adequate treatment according to medical standards. The patient will be discharged from the investigational site only after resolution of ECG findings as assessed by the Investigator.

In case of occurrence of symptoms suggestive of arrhythmia related to QTcF prolongation, a cardiologic evaluation will be performed, and treatment will be provided according to medical standards at the discretion of the Investigator.

In order not to confuse an ECG recording, PK samples should be taken after performing the ECG.

The centralised ECG evaluation will include the semi-automatic determination of the RR, PR interval, QRS complexes, and QT intervals.

All interval measurements in one patient will be performed on the same lead. The intervals will be measured from four cardiac cycles (beats) in lead II. If lead II shows a flat T wave or is not measurable for any reason, lead V5 will be used, or if that lead is not measurable, then lead I will be used.

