Central morphological analyses of the ECGs (cardiologic assessments) will be performed by a board-certified cardiologist or equivalent. The cardiologist will interpret one ECG per time point. In case of triplicate ECG recordings per time point, this ECG will be selected randomly. In case additional (unscheduled) ECGs due to safety reasons are recorded at the study site, all ECGs of this time point including the additional ECGs will undergo interpretation. The ECG interpretation will include an overall assessment (normal, abnormal, not assessable) as well as assessments concerning rhythm, conduction, presence of myocardial infarction, ST segment deviations, T wave morphology, and U wave morphology findings.

Abnormalities detected during centralised ECG evaluation will not necessarily qualify as AEs. In case of clinically relevant abnormalities (e.g., heart blocks or large changes in interval duration) the ECG core laboratory may contact the Investigator and vice versa.

Centrally assessed ECGs will comply with the ICH E14 guidance document and supplements (R05-2311, R13-0801, R13-4095) as well as the FDA requirements for annotated digital ECGs (R09-4830).

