7.8.4 ECG

For all 3 trial parts, analyses of ECG will be descriptive in nature. Newly emergent abnormalities will be recorded and analysed as adverse events.

In addition, statistical ECG analyses will be performed for the centrally evaluated digital ECG recordings as follows.

Derivation of ECG variables

Three replicate digital ECG recordings will be collected as specified in the flowchart of the CTP. Each of the three recorded single ECGs will then be evaluated semi-automatically for cardiac intervals, which comprise the RR, PR and QT interval and the QRS complex. Measurements of these intervals will be made on four (possibly consecutive) cardiac cycles from the lead chosen (usually lead II). The measurements of the cardiac cycles will be stored in the database, i.e. usually 12 values per time point. The four cardiac cycles will be averaged prior to the calculation of the heart rate and heart rate corrected QT intervals (QTc).

The heart rate will be derived from the RR interval as

$$\text{HR [beats/min]} = 60000/\text{RR [ms]}$$

Heart rate corrected QT intervals (generally denoted by QTc) will be calculated using Fridericia's (QTcF) formula and Bazett's formula (QTcB):

- $\text{QTcF [ms]} = (1000/\text{RR})^{(1/3)} * \text{QT [ms]}$
- $\text{QTcB [ms]} = (1000/\text{RR})^{(1/2)} * \text{QT [ms]}$

Further aggregation of the three replicate ECG intervals and HR at each scheduled time point will then be performed using arithmetic means. Additional averaging over 1-3 time points will be performed to derive the baseline values: they will be calculated as the mean values of the 1-3 triplicate ECG recordings collected pre-dose on Day 1. These mean values will be used for the derivation of the ECG variables as they are specified in [Section 5.4.3](#).

[figure not shown]
ECG analyses

[figure not shown]
For all ECG variables, listings of individual data will be shown in the appendix of the CTR. Absolute values and changes from baseline in QTcB interval as well as the percentage changes for PR interval and QRS complex will only be displayed in listings.

Absolute values and changes from baseline in QTcF interval, QT interval, HR, PR interval, and QRS complex will be summarised descriptively by treatment, cycle, day, and time point using the ECG set. The time profiles of mean and standard deviation for the absolute values and changes from baseline on treatment will be displayed graphically by treatment.

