Frequency tables will be provided for all categorical variables including notable findings and qualitative ECG findings. The tables will be presented separately for the visit days where an ECG profile has been taken as well as for the overall on-treatment period using the maximum value per patient. Frequencies of the increases in QTcF and QT intervals above thresholds as defined in Section 5.4.3 between baseline and on-treatment will be displayed in two-way shift tables by treatment. Frequency tables with regard to the new onset of qualitative (morphological) ECG findings will display categories of grouped findings based on the CDISC (EGTEST) terminology as well as the frequencies per each observed type of finding. These descriptive analyses will be performed for patients in the ECG Set separately for Part A, B and C.

For all patients with any notable finding (see Section 5.4.3), a separate listing in Section 15 of the CTR will be created and the corresponding time profiles will be shown. Notable findings of patients in the TS who are excluded from the ECG Set will be listed in separate listings.

[figure not shown]

[figure not shown]

[figure not shown]

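### Unscheduled safety ECGs fall outside the SAP's ECG on-treatment period, so the QTcF/QT maximum, threshold, notable-finding and new-onset tables can only understate outliers

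*SAP*

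**What the plan says.** SAP 5.4.3 gives ECG its own on-treatment definition: "the on-treatment period refers to all scheduled time points with centrally evaluated ECG recordings following the first administration of trial medication in Cycle 1". The outlier outputs are built on it:

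- QTcF and QT are categorised by visit day and "for the overall on-treatment period using the maximum value per patient within the considered period".
- Notable findings start from the same values: "A notable finding in QT/QTcF interval in any on-treatment value for a given patient is defined as". The list that follows also covers PR and QRS increases.
- New-onset morphology means a finding seen on treatment but not at baseline.

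SAP 7.8.4 derives the values ("Further aggregation of the three replicate ECG intervals and HR at each scheduled time point will then be performed using arithmetic means") and tabulates the categories for "the overall on-treatment period using the maximum value per patient". SAP 4 records a change made because the time of maximum concentration came earlier than expected: "all ECG recordings collected at the scheduled time points listed in Tables 10:3:1, 10:3:2 and 10:3:3 of the CTP will be analysed".

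Protocol 5.2.4 expects more recordings than the schedule holds. After related ECG changes, or whenever the investigator sees a need, "additional ECG monitoring will be performed in the respective and later courses of treatment". ECGs go to a central vendor, whose data serve the retrospective analysis. The paragraph on central cardiologist reading addresses off-schedule recordings directly: "In case additional (unscheduled) ECGs due to safety reasons are recorded at the study site", those ECGs are interpreted too. Protocol 7.3.4 leaves the analysis of centrally evaluated ECGs to the SAP.

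**The concern.** A safety ECG taken off schedule is often taken because something already looked abnormal. It is a plausible place for a patient's longest QTcF or a new morphological finding. If the word scheduled is applied as written, these recordings drop out of the tables meant to show extremes, while the tables keep the label of the overall on-treatment period.

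The protocol synopsis lists QTcF evaluation among the safety criteria, so a reader of the report will look to these tables. A patient whose only notable value is off schedule would also be missing from the separate listing and time profiles that SAP 7.8.4 promises for patients with notable findings.

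ECG is also the exception within the SAP. SAP 6.1 runs the general safety period from first dose to 30 days after last dose, and SAP 7.8.2 applies the adverse-event period to laboratory values. Neither depends on whether the assessment was scheduled, and no reason is given for treating ECG differently.

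**Working it through.** The plan gives no figure to reproduce. The check traces the definition through to the outputs and compares it with the protocol.

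1. **Definition.** SAP 5.4.3 sets two conditions for an on-treatment ECG: a scheduled time point after first dose, and central evaluation. An unscheduled ECG fails the first even when it meets the second.

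2. **Outputs that inherit it.** The threshold categories (QTc at 450, 480 and 500 ms; QT at 500 ms; change from baseline at 30 and 60 ms for QTc and 60 ms for QT), the per-patient maximum, the notable findings and new-onset morphology all use on-treatment values.

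3. **Search for an exception.** SAP 4 names scheduled time points. SAP 6.6 covers missing cardiac cycles, missing replicates and missing baseline. SAP 6.7 covers baseline. SAP 7.8.4 averages at scheduled time points. None of the visible text admits an unscheduled recording.

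4. **What the protocol supplies.** For morphology, central reading of unscheduled safety ECGs is explicit in protocol 5.2.4. For intervals, it follows only from the general sentence that ECGs are sent to the central vendor. The same section limits direct review to the baseline, 6-, 8- and 24-hour readings.

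5. **Direction.** Let S be a patient's scheduled post-dose values and A all centrally evaluated post-dose values. S is a subset of A, so max(S) ≤ max(A). Omission can lower the category or leave it alone. Hypothetical example: all scheduled QTcF values, baseline included, are at most 450 ms, and one unscheduled value is 510 ms. By the SAP the maximum is at most 450 ms, the lowest category, with no new onset above 500 ms. With the unscheduled value the maximum is 510 ms, the patient is in the >500 ms category, and this is a notable finding by new onset.

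6. **Leverage in the planned tables.** SAP 6.1 presents results by dose cohort. Assume, for scale only, ECG Set cohorts as large as the evaluable cohorts in protocol Table 7.1.2: 5 (6, 8 and 5 patients in Part B). One reclassified patient then moves a cohort's proportion by 1/8 = 12.5 to 1/5 = 20 percentage points. The documents do not say that any such patient exists.

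7. **Reach of the schedule.** In protocol Table 10.3: 1, the post-dose ECG time points are 9 on Day 1, 1 on Day 2, 10 on Day 15 and 1 on Day 16: 9 + 1 + 10 + 1 = 21, all in Cycle 1. The Part A and Part B flow charts also schedule ECGs in Cycle 2, from Cycle 3 onwards and at end of treatment.

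**The case against.** **Adverse events already cover the patient.** SAP 5.4.3 makes adverse-event analysis the route for clinically relevant ECG findings and presents the statistical tables as an addition. Protocol 5.2.4 has the investigator check recordings, grade QTcF prolongation by CTCAE and report what is clinically relevant. This stands, and it limits the point to descriptive tables. It does not remove it: an adverse-event table is not a numerical outlier table, and protocol 5.2.4 notes that abnormalities found centrally need not become adverse events.

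**The trigger is usually already counted.** The protocol starts further monitoring when the mean of three ECGs exceeds 500 ms, and triplicates are tied to scheduled sampling. A patient who crosses that line at a scheduled triplicate is already in the top category. This stands for that route. It does not cover extra ECGs taken after other related changes or at the investigator's discretion, nor new morphology.

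**Mixing recordings is untidy.** Unscheduled ECGs may be single rather than triplicate, and they give some patients more chances of a high maximum. That is fair, and a reason for a footnote and a side-by-side count. The SAP already accepts fewer replicates: SAP 6.6 averages over 1 or 2 recordings when others are missing.

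**A stronger reading goes too far.** Because the tables cited in SAP 4 stop at Cycle 1 Day 16, a reader might infer that the overall on-treatment results describe only four days of Cycle 1. The documents do not establish this. SAP 5.4.3 covers all scheduled, centrally evaluated time points; the flow charts schedule later ECGs; SAP 7.8.4 summarises by cycle as well as day; and SAP 4 reads as widening the set of readings, not as dropping later visits. What remains is an ambiguity worth one sentence.

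**Conclusion.** The point holds for the overall on-treatment maxima, threshold categories, notable findings and new-onset morphology in Parts A and B (SAP 4 cancels Part C, which enrolled no patients). Followed as written, the SAP leaves out unscheduled safety ECGs, and the resulting error has one direction, towards fewer outliers. Its size is unknown, because the documents do not say how many unscheduled ECGs were made or measured.

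A reader might infer a size by pooling the evaluable patients of both parts and setting a confidence limit on the >500 ms rate. That would match no planned output: the SAP uses the ECG Set, reports the parts and cohorts separately, and shows no interval for these tables. A reader might also infer that the vendor has certainly measured QTcF on every unscheduled ECG. The text is explicit only for morphology.

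The conclusion assumes that the parts of SAP 7.8.4 not shown contain no rule bringing unscheduled recordings in. It is an inexpensive improvement to the ECG tables. It does not show that ECG safety goes unreported.

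**What to change.** In SAP 5.4.3, separate two uses.

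- **By-time-point summaries, mean profiles and exposure-response:** scheduled time points, as now.
- **Per-patient maxima, threshold categories, notable findings and new-onset morphology:** every post-dose ECG with a central evaluation, scheduled or not, up to 30 days after last dose. Require central interval measurement for QTcF/QT and central interpretation for morphology. Show the scheduled-only count beside the full count, and footnote the unequal numbers of recordings and the mix of single and triplicate ECGs.

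Align the derivation text in SAP 7.8.4, and state in SAP 4 that scheduled ECGs from later cycles and the end-of-treatment visit are included where centrally evaluated.

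The cost is SAP wording, a flag in the ECG dataset and one extra column. No new ECGs or readings are needed, because a recording without the relevant central evaluation stays out. If few unscheduled ECGs were measured centrally, the interval tables will hardly change, and the footnote should say so.
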